4.8. Randomization

Eligible patients who develop a CARV infection after lung transplantation will need to provide written informed consent prior to study participation and will undergo randomization using a computer-generated method with a 1:1 ratio, and stratified by BOS stage (group 1: BOS stages 0 and 0p vs. group 2: BOS stages 1 and 2) to one of the treatment assignments: (1) inhaled beclomethasone, or (2) placebo. The site will aim to randomize patients within 7 days of identification of CARV infection.

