4.10. Outcomes Assessment

The development of CLAD is defined according to the following criteria:

- CLAD: FEV_1 and/or $FVC \leq 80\%$ baseline on 2 measurements obtained 3 weeks apart

Once CLAD has been established, it will be further defined by the following criteria:

- Restrictive CLAD (RAS): $FVC \leq 80\%$ baseline on 2 measurements obtained 3 weeks apart with an FEV_1/FVC ratio $\geq 75\%$
- Obstructive CLAD (BOS): $FEV_1 \leq 80\%$ baseline on 2 measurements obtained 3 weeks apart

Progressive CLAD is defined as a $\geq 15\%$ decrement in pre-CARV infection baseline FEV_1 or FVC . The pre-CARV infection baseline FEV_1 and FVC are defined as the average of the 2 most recent FEV_1 or FVC measurements separated by at least 3 weeks, and occurring within the 6 months prior to the diagnosis of the CARV infection. In the event that only 1 FEV_1 or FVC measurement is available in the previous 6 months, that value will serve as the pre-CARV infection baseline FEV_1 or FVC .

5. Treatments

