5.1. Randomized Treatment Assignment

Randomization will occur using an automated online system that will reveal assignment group only after investigator/study staff have confirmed eligibility. The system will automatically send the participant study ID number and randomized treatment group assignment to the study pharmacist.

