6.5. Testing for Antibodies to Self-antigens and Inflammatory Cytokines

At the same time points that testing is conducted for DSA (enrollment and months 1, 3 and 6 [\pm 10 days for each time point]), participants will be tested for the development of antibodies to collagen V and K- α 1 tubulin. In addition, participants' serum will be tested for a battery of pro-inflammatory and anti-inflammatory cytokines. This will be conducted in [name] research laboratory.

7. Statistical Considerations

We estimate an incidence of new or progressive CLAD of 50% at 6 months after CARV infection in the placebo group and an absolute risk reduction of 25% in the inhaled beclomethasone group. Therefore, a sample size of 40 subjects would provide 80% power. The primary endpoint of the development or progression of CLAD or death at 6 months will be evaluated as a binary endpoint and will be analyzed using the chi-squared method. In addition, the primary endpoint will be evaluated as a time to event analysis using the Kaplan-Meier method and the two groups will be compared using the log rank test. Secondary endpoints consisting of continuous data will be analyzed using either the Student's t-test or Mann-Whitney U Test and those consisting of categorical data will be analyzed using the chi-squared method.

8. Ethical Considerations and Safety

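### Randomization is stratified by BOS group but the primary tests ignore it: a minor, inexpensive alignment, with a power gain whose size and sign the documents do not settle

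*Combined protocol and SAP*

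**What the plan says.** Protocol section 4.8 states that patients "will undergo randomization using a computer-generated method with a 1:1 ratio", "stratified by BOS stage (group 1: BOS stages 0 and 0p vs. group 2: BOS stages 1 and 2"). Section 5.1 adds only that "Randomization will occur using an automated online system". Neither section mentions blocks or any other device for keeping the arms balanced within a BOS group.

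Section 7 is the only statistical section. It says the primary endpoint "will be evaluated as a binary endpoint and will be analyzed using the chi-squared method", and for the time-to-event version that "the two groups will be compared using the log rank test". It names no stratified test, no adjustment for BOS group, and no reason for leaving the factor out. Its planning assumption is 50% incidence on placebo and "an absolute risk reduction of 25% in the inhaled beclomethasone group".

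Section 4.10 judges the two kinds of CLAD event by different rules. New CLAD needs FEV1 and/or FVC at or below 80% of "baseline on 2 measurements obtained 3 weeks apart". Progressive CLAD is a 15% or greater "decrement in pre-CARV infection baseline FEV_1 or FVC".

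**The concern.** Analysis normally follows the randomization. When arms are balanced within strata and the stratification factor predicts outcome, the design removes between-stratum variation from the treatment comparison. An unstratified chi-squared test still counts that variation in its variance, so it is conservative and may forgo power. In a trial of 40 patients, spare power is scarce.

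Prespecification is also at stake. Section 7 is silent, so a BOS-stratified result introduced after unblinding would look chosen from the data.

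**Working it through.** **Inputs from the documents.** 40 patients at 1:1, so 20 per arm; 50% vs 25% (section 7); two BOS strata (section 4.8); a two-sided alternative (section 4.2).

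**Assumptions.** Alpha 5% (none is stated); no dropout; all stratum sizes, rates and effect patterns. A gap is the difference in risk between the two strata (placebo risk in the power calculations). A split such as 14+6 means 14 lower-risk and 6 higher-risk patients per arm.

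**1. The plan's own power figure.** The pooled risk is 0.375. The null standard error is √(2 × 0.375 × 0.625 / 20) = 0.153. The alternative standard error is √((0.50 × 0.50 + 0.25 × 0.75) / 20) = 0.148. Power is Φ((0.25 − 1.96 × 0.153) / 0.148) = Φ(−0.34), about 37%, not the stated 80%. Exact enumeration of the uncorrected chi-squared test gives 37.5%. I use this only as the reference level here.

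**2. Why the unstratified test is conservative.** With exact balance within strata, the true variance is the pooled variance times Σ wₖpₖ(1 − pₖ) / [p̄(1 − p̄)]. For equal strata at 30% and 70% the ratio is 0.21 / 0.25 = 0.84, so the large-sample level is 2Φ(−1.96 / √0.84) = 3.2%. At 40% and 60% the ratio is 0.96 and the level is 4.5%.

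**3. Exact level at this sample size.** Full enumeration of the four binomial counts, 10+10 per arm, no continuity correction, critical value 3.841:

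| Overall null risk | Test | Gap 0 | 20 | 30 | 40 |
|---|---|---|---|---|---|
| 50% | chi-squared | 4.3% | 3.8% | 3.3% | 2.6% |
| 50% | CMH | 4.2% | 4.4% | 4.6% | 4.8% |
| 25% | chi-squared | 5.1% | 4.5% | 3.8% | 2.8% |
| 25% | CMH | 4.9% | 4.8% | 4.8% | 4.9% |

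The 4.3% at no gap comes from discreteness, not stratification. Discreteness can also act the other way: the chi-squared level is 5.3% when both strata have risk 30%.

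**4. Power change, CMH minus chi-squared (points).** Exact balance. The placebo average is 50%, and a common odds ratio is solved so that the treated average is 25%:

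| Split per arm | Gap 0 | 10 | 20 | 30 | 40 |
|---|---|---|---|---|---|
| 10+10 | −2.0 | −1.4 | +0.2 | +2.6 | +5.6 |
| 14+6 | −2.2 | −1.6 | −0.3 | +2.0 | +5.3 |
| 6+14 | −2.2 | −1.8 | −0.6 | +1.4 | +3.8 |
| 16+4 | −2.2 | −2.1 | −1.1 | +0.8 | +4.0 |
| 4+16 | −2.2 | −1.6 | −0.3 | +1.5 | +3.7 |

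For 10+10 at gap 40, power goes from 36.4% to 42.0%.

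**5. If the odds ratio is not common.** 10+10, placebo 35% and 65%:

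- Treated 10% / 40% (equal risk difference): +4.0.
- Treated 25% / 25%: −0.4.
- Treated 35% / 15% (all benefit in the higher-risk stratum): −2.0.

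I also scanned treated rates that average 25% with neither stratum harmed, at gaps of 20 to 40. The worst losses are about 2.2 points (10+10), 3.0 (14+6) and 3.5 (16+4). The last occurs at placebo 42% / 82% and treated 31% / 1%.

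**6. If allocation is not blocked.** By simulation, the chi-squared level returns to 5.0–5.2%. The CMH power change at gaps 0/20/30/40 is −2.0/−1.0/+0.4/+2.4 points with equal strata and −2.0/−1.3/−0.2/+1.8 with 80/20 strata.

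**7. Log-rank.** By simulation with exponential times, censoring at 6 months, a common hazard ratio and exact 10+10 balance, at gaps 0/20/30/40:

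- The unstratified level is 5.2/4.7/4.1/3.3%. The stratified level is 5.1–5.4%.
- The power change from stratifying is −0.2/+1.2/+3.0/+5.9 points.
- Without blocking, the change runs from −1.1 to +3.7 points with equal strata.

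**The case against.** The best defence is that no harm from the plan is shown. The chi-squared test keeps its level. The power gain needs three things the documents do not supply: balance within strata, a strongly prognostic BOS group and similar odds ratios in both groups. Over the lower half of the gap range CMH has less power, and without blocking a clear gain appears only at a gap of 40 points. In a self-described pilot with about 37% power, a sentence justifying the unstratified test, or a stratified sensitivity analysis, might be enough.

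Most of this stands, and it is why the point is minor. What remains is that design and analysis differ without explanation, and that the choice is best closed before unblinding. Stratified randomization usually implies blocking, but the text does not say so.

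A reader might infer from section 4.10 that BOS group must be prognostic, because new and progressive CLAD are judged by different rules. Those rules allow event rates to differ between strata, but they fix neither direction nor size. They also make a common odds ratio less certain. That the sponsor chose BOS group as the only stratification factor suggests it was expected to matter, but gives no rate.

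**Conclusion.** The mismatch between sections 4.8 and 7 is real, and it is minor. With strata balanced and BOS group clearly prognostic, the chi-squared test is conservative, down to 2.6–2.8% at a 40-point gap with 10+10 per arm. Any gain from CMH is at most about 6 points in the cases examined; the worst loss is about 3.5 points. Which applies cannot be read from the documents, which give no blocking, stratum sizes, stratum event rates or stratum effects.

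Three stronger readings are not supported:

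- That the unstratified tests are invalid or inflate false positives. They do not; the small excess over 5% in some null cases is discreteness.
- That the plan certainly loses power. Even the sign depends on assumptions.
- That stratifying would rescue the sample size. CMH power stays between about 33% and 42% in the exact-balance cases above, so the 80% claim must be dealt with separately.

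**What to change.** In section 7:

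- Name a CMH test stratified by the BOS group used at randomization as the primary binary analysis.
- Name a log-rank test stratified by the same factor for the time-to-event analysis.

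In section 4.8 or 5.1, state whether allocation is blocked within the BOS strata; block sizes can stay concealed. If the sponsor prefers the unstratified tests, a sentence giving the reason would close the question.

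The cost is wording only, because BOS group is already needed to randomize. The statistical downside is about 2 points of CMH power if BOS group is not prognostic, and up to about 3.5 points in the worst effect pattern. The stratified log-rank loses at most about 1 point if BOS group is not prognostic.

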4.3. Study Objectives

Primary Objective

- To determine if inhaled beclomethasone has greater efficacy than placebo in preventing the composite endpoint of new or progressive CLAD or death 6 months after CARV infection in adult lung transplant recipients.

Secondary Objectives

- Incidence of new or progressive CLAD at 6 and 12 months after CARV infection
- Time to development or progression of CLAD
- Safety and tolerability of inhaled beclomethasone
- Respiratory viral symptoms
- Development of donor-specific HLA antibodies (DSA)
- Change in DSA mean fluorescence intensity
- Development of antibodies to lung-specific self-antigens (Collagen V and K- α 1 tubulin)
- Serum cytokine profiles
- Peripheral immune cell phenotypes
- Incidence of other bacterial, viral, or fungal infection at the time of CARV infection
- Incidence of acute rejection and lymphocytic bronchiolitis within 6 months following CARV infection
- Survival at 6 months (+ 10 days) and 12 months (+ 10 days) after CARV infection

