6.4. HLA Antibody Testing

Participants will be tested for the development of donor-specific HLA antibodies (DSA) at enrollment, and at months 1, 3 and 6 (\pm 10 days for each time point) after CARV infection using the clinical assay in our center's histocompatibility laboratory. This will require a blood draw at those time points.

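### Section 7 analyses change in DSA MFI and serum cytokines with unadjusted two-group tests; using the enrollment value and BOS stratum as covariates would add precision at no data cost

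*Combined protocol and SAP*

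**What the plan says.** - Section 7 (Statistical Considerations): "Secondary endpoints consisting of continuous data will be analyzed using either the Student's t-test or Mann-Whitney U Test". It names no covariate, stratum or term for repeated visits, and does not say how to choose between the two tests.
- Section 4.3 (Study Objectives) lists "Change in DSA mean fluorescence intensity" and "Serum cytokine profiles" as secondary objectives; Section 4.9.2 repeats both. The first is a difference from an earlier value. For the second, the plan does not say whether levels or changes are compared, or at which visit.
- Section 6.4 schedules DSA testing "at enrollment, and at months 1, 3 and 6". Section 6.5 begins "At the same time points that testing is conducted for DSA (enrollment and months 1, 3 and 6" for the self-antigen antibodies and adds that "participants' serum will be tested for a battery of pro-inflammatory and anti-inflammatory cytokines", which I read as the same schedule.
- Section 4.8 has randomization "stratified by BOS stage (group 1: BOS stages 0 and 0p vs. group 2: BOS stages 1 and 2". No analysis in Section 7 uses this factor.

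**The concern.** The trial plans 40 patients, about 20 per arm, so the biomarker comparisons have little information to spare. The plan collects two pieces of information that could sharpen them, the pre-treatment level and the BOS group, and uses neither as a covariate.

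The two simple analyses that Section 7 allows are weak at opposite ends. A change-score test does poorly when enrollment and follow-up values are weakly correlated, because subtraction adds noise. A follow-up-only test does poorly when they are strongly correlated, because it ignores a good predictor. The correlation is unknown in advance, and for cytokines the plan does not say which of the two is intended. A covariate-adjusted analysis removes the need to choose.

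**Working it through.** The documents give no precision or power figure for these biomarkers, so there is nothing to reproduce first. Section 7's one power figure concerns the primary binary endpoint and does not bear on this point.

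**Inputs from the documents.** 40 patients, 1:1, so 20 per arm (Section 1); two-sided alternative (Section 4.2); enrollment and follow-up samples (Sections 6.4, 6.5); two BOS strata (Section 4.8).

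**Assumptions.** Two-sided alpha 0.05; correlation rho between enrollment and follow-up values of 0.3, 0.5, 0.7 or 0.9; equal variances at the two times; a true difference of 0.8 SD; permuted blocks of 4 within strata; the size of the BOS effect and the stratum split.

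**Step 1: variance of the treatment difference**, relative to a follow-up-only test (= 1):

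- change score: 2(1 − rho)
- ANCOVA: 1 − rho²
- ANCOVA relative to change score: (1 − rho²) / (2(1 − rho)) = (1 + rho)/2

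| rho | ANCOVA / change | Reduction | ANCOVA / follow-up | Reduction |
|---|---|---|---|---|
| 0.3 | 0.65 | 35% | 0.91 | 9% |
| 0.5 | 0.75 | 25% | 0.75 | 25% |
| 0.7 | 0.85 | 15% | 0.51 | 49% |
| 0.9 | 0.95 | 5% | 0.19 | 81% |

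Simulation with n = 40 and both covariates in the model gives slightly smaller reductions: 34%, 23%, 13%, 2% against change and 6%, 23%, 48%, 81% against follow-up.

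**Step 2: power at 0.8 SD** (simulated, normal data, 20,000 runs; type I error 4.7% to 5.1% for all three methods):

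| rho | Follow-up t-test | Change t-test | ANCOVA | Gain over better simple test |
|---|---|---|---|---|
| 0.3 | 69.6% | 54.8% | 72.7% | 72.7 − 69.6 = 3 points |
| 0.5 | 69.4% | 69.7% | 80.3% | 80.3 − 69.7 = 11 points |
| 0.7 | 69.6% | 89.1% | 92.4% | 92.4 − 89.1 = 3 points |
| 0.9 | 69.3% | >99% | >99% | about 0 |

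Log-normal data behave much the same. At rho 0.3, 0.5 and 0.7, Mann-Whitney on follow-up has 68%, 67% and 68% power, Mann-Whitney on raw change 57%, 68% and 87%, and ANCOVA on logs 74%, 80% and 92%. The largest gain over the better simple test is 80.0 − 67.8, about 12 points. At rho 0.9 Mann-Whitney on change and ANCOVA both exceed 99%.

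**Step 3: the BOS stratum** (rho 0.5, enrollment value in the model throughout; ranges cover 50:50 and 75:25 splits):

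| BOS effect on biomarker | Power without BOS | Power with BOS | Type I error without BOS |
|---|---|---|---|
| none | 80% | 80% | 4.9% |
| 0.5 SD | 77–78% | 80% | 4.2–4.3% |
| 1 SD | 71% | 79–80% | 2.5–3.1% |

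With BOS in the model, type I error is about 5% throughout. Leaving BOS out never inflates the error rate; it makes the test conservative when BOS matters.

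**Step 4: many zero MFI values.** Development of DSA is itself an endpoint, so some patients are expected to be negative at enrollment. Simulations with an assumed 50% to 80% zeros compared rank-based ANCOVA with Mann-Whitney on change. Rank ANCOVA gains about 6 to 15 points at rho 0.3 to 0.5, is about equal at 0.7, and loses 1 to 5 points at 0.9 (for example 97 v 99%, 89 v 93% and 80 v 85% at 50%, 70% and 80% zeros).

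**The case against.** The strongest case is that this is a preference and not an error. The planned tests are valid, the endpoints are secondary biomarkers in a single-center pilot, and the primary endpoint is untouched. All of that stands, and it is why the point is optional.

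The size also rests on assumed values. The 81% figure is against a follow-up-only test, which the change definition rules out for MFI and which is only one reading for cytokines. Against the better simple test the gain is modest. At a smaller assumed difference of 0.5 SD, ANCOVA reaches 36%, 42%, 57% and 94% power against 34%, 34%, 51% and 93% for the better simple test, so at correlations of 0.3 to 0.7 the comparison stays underpowered either way. The larger BOS gain needs a 1 SD stratum effect on a serum biomarker, for which the documents offer no support. These limits stand too. They reduce the benefit but do not remove it, and the covariates are already collected.

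The zero-heavy objection holds in part: the advantage of adjustment does not extend to every correlation when many MFI values are zero.

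A reader might infer that the plan discards the enrollment value altogether. The documents do not support that. MFI is defined as a change, so an earlier value, presumably enrollment, is subtracted; for cytokines, baseline use is unspecified and not shown to be excluded.

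**Conclusion.** The point holds as a matter of efficiency. No planned analysis uses the enrollment value as a covariate, and none uses the BOS stratum. A reader might go further and infer bias or an inflated false-positive rate; neither follows, since the simple tests keep their type I error at or below the nominal level.

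For roughly continuous data with equal variances and rho between 0.3 and 0.9, ANCOVA's variance is 5% to 35% below a change-score test and 9% to 81% below a follow-up-only test. At 0.8 SD with 20 per arm, the gain over the better simple test is about 0 to 11 points of power (up to about 12 in the skewed case). Adding BOS gains nothing if it does not predict the biomarker and roughly 8 to 10 points if its effect is 1 SD. Rho, the treatment difference, the BOS effect, the stratum split and the share of zeros are all assumptions. This is a low-priority improvement that could be made, not a defect that must be repaired.

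**What to change.** In Section 7, state that serum cytokines and DSA MFI at months 1, 3 and 6 (log scale if skewed) will be analysed by ANCOVA or a repeated-measures model, with the enrollment value and BOS group as covariates and Mann-Whitney as a sensitivity analysis. This also settles how the cytokine enrollment value is used. If many MFI values are zero, specify rank-based ANCOVA or keep Mann-Whitney on change, and do not claim a gain at every correlation, since rank ANCOVA can be slightly less powerful when the correlation is very high.

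The cost is about two sentences of text, a little more programming, two degrees of freedom, and a stated rule for patients without an enrollment sample. No new data, visits or patients are needed.

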Protocol:

A randomized placebo controlled trial of inhaled beclomethasone after community-acquired respiratory viral infection in lung transplant recipients

Version: 5

Date: 5.28.15

1. Abstract

The randomized placebo controlled trial of inhaled beclomethasone after community-acquired respiratory viral (CARV) infection in lung transplant recipients is a single center pilot study evaluating the impact of inhaled beclomethasone on the development and progression of chronic lung allograft dysfunction (CLAD) or death after CARV infection. The study will randomize 40 subjects to inhaled beclomethasone or placebo in a 1:1 ratio, and follow-up will be complete 12 months after randomization. The primary objective of the study is to determine if inhaled beclomethasone has greater efficacy than placebo for the endpoint of CLAD development or progression or death after randomization. The study will also assess multiple secondary endpoints including the safety and tolerability of inhaled beclomethasone in lung transplant recipients, respiratory viral symptom scores, the development of donor-specific human leukocyte antigen antibodies and antibodies to lung-specific self-antigens, and survival.

2. Background

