4.1. Primary Aim

To conduct a single center, pilot, randomized placebo controlled trial that compares the efficacy and safety of inhaled beclomethasone versus placebo to prevent the development or progression of CLAD, or death after CARV infection in lung transplant recipients.

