4.2. Hypotheses

Null Hypothesis There is no difference in incidence of new or progressive CLAD, or death between the two randomized treatment groups (placebo = inhaled beclomethasone)

Alternative There is a statistically significant difference in the incidence of new or progressive CLAD, or death between the two randomized treatment groups (placebo ≠ inhaled beclomethasone)

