4.5. Setting

This single center trial will enroll 40 patients from Washington University School of Medicine and Barnes-Jewish Hospital academic lung transplant center. Screening, participant consent, treatment, and data collection will be conducted at this transplant center.

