4.9.2. Secondary Endpoints

Incidence of new and/or progressive CLAD, safety and tolerability of inhaled beclomethasone, respiratory virus symptom score, development of DSA, change in DSA mean fluorescence intensity, development of antibodies to

self-antigens, serum cytokine profiles, peripheral immune cell phenotypes, incidence of other bacterial, viral, or fungal pulmonary infections at the time of CARV infection, incidence of acute rejection and lymphocytic bronchiolitis within 6 months (+ 10) days after CARV infection, incidence of new or progressive CLAD within 12 months (+ 10) after CARV infection, and survival 6 months (+ 10 days) and 12 months(+ 10 days) after CARV infection.

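### The aim includes a comparison of safety, but the only between-arm analysis stated for categorical safety data is a chi-squared test, with no effect estimate or interval, in about 20 patients per arm

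*Combined protocol and SAP*

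**What the plan says.** Section 4.1 of the combined protocol and SAP describes a pilot trial that "compares the efficacy and safety of inhaled beclomethasone versus placebo". Elsewhere safety is secondary: section 4.3 lists "Safety and tolerability of inhaled beclomethasone" among the secondary objectives, and section 4.9.2 opens its list with "Incidence of new and/or progressive CLAD, safety and tolerability of inhaled beclomethasone". Survival at 6 and 12 months is a separate item in both lists. The hypotheses in section 4.2 and the primary endpoint in section 4.9.1 concern CLAD or death only.

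Section 7 has no paragraph on safety. Safety data fall under its general rule for secondary endpoints. Continuous measures are to be compared by a t-test or a rank test; for the remaining endpoints the rule is that "those consisting of categorical data will be analyzed using the chi-squared method". It requests no effect estimate, confidence interval or limit on excess harm.

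Sections 8.4.1 to 8.4.5 define SAEs and cover their collection, the investigator's judgement of relatedness, reporting, treatment and discontinuation of study drug. None of them says how the two arms will be compared.

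On size, the abstract states: "The study will randomize 40 subjects to inhaled beclomethasone or placebo in a 1:1 ratio".

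**The concern.** A comparative safety question asks how much extra harm the data allow. A test of difference answers another question, namely whether the observed imbalance is larger than chance would readily produce. With about 20 patients per arm, the second question will often get the answer no even when the drug raises risk substantially.

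If Section 7 is followed literally, the between-arm safety result is a set of p-values. Many would be non-significant whether or not inhaled beclomethasone causes excess harm in these immunosuppressed patients. A reader of the report could not tell from them whether an excess of 5 or of 25 percentage points remained possible.

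**Working it through.** **The plan's own figure.** There is none for safety. The only power statement in Section 7 (80% with 40 subjects) concerns efficacy at 50% versus 25%. The exact calculation used below gives about 37% for that comparison at 20 per arm, so the 80% cannot be carried over to safety. That discrepancy is a separate matter.

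**Inputs.**
- Sample size: 40 patients, 1:1 (abstract; section 4.5), so n = 20 per arm.
- Test: chi-squared (Section 7), taken as uncorrected Pearson because no correction is mentioned.
- Alpha: not stated. Section 4.2 says only "There is a statistically significant difference in the incidence". I assume 0.05, two-sided.
- SAE rate on placebo: not stated. I assume a range of 5% to 40%.

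**Test statistic.** With a and b events in the two arms and pooled proportion p̄ = (a + b)/40,

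X² = (a/20 − b/20)² / [p̄(1 − p̄) × 2/20], significant if X² ≥ 3.841.

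**Miss rate for a doubling.** For each pair of true rates, I summed the binomial probabilities of all 21 × 21 possible outcomes with X² below 3.841.

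| Placebo v active | Power | Missed |
|---|---|---|
| 5% v 10% | 5% | 95% |
| 10% v 20% | 14% | 86% |
| 20% v 40% | 29% | 71% |
| 30% v 60% | 46% | 54% |
| 40% v 80% | 75% | 25% |

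Normal-approximation check at 20% v 40%: p̄ = 0.30; null SE = √(2 × 0.30 × 0.70/20) = 0.1449; alternative SE = √[(0.20 × 0.80 + 0.40 × 0.60)/20] = 0.1414. Then z = (0.20 − 1.96 × 0.1449)/0.1414 = −0.59, so power is about 28% and the miss rate 72%, in line with the exact 71%. With Yates' correction the miss rate at these rates is 82%, and with Fisher's test 81%. For 80% power at 20% v 40%, about 82 patients per arm are needed.

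**What an interval would show.** The Newcombe interval combines the Wilson limits (l, u) of each arm's proportion p. The upper limit for the difference is d + √[(u₁ − p₁)² + (p₂ − l₂)²]; the lower limit is d − √[(p₁ − l₁)² + (u₂ − p₂)²].

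- *4/20 v 4/20:* the Wilson limits are 0.081 and 0.416 in each arm. The upper limit is 0 + √(0.216² + 0.119²) = 0.247. Identical counts still allow an excess of about 25 percentage points.
- *9/20 active v 4/20 placebo:* d = 0.25, X² = 2.85, p = 0.09, so not significant. The Wilson limits for 9/20 are 0.258 and 0.658. The lower limit is 0.25 − √(0.192² + 0.216²) = −0.039, and the upper is 0.25 + √(0.208² + 0.119²) = 0.490. The interval runs from −4 to +49 points.

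In both examples the chi-squared rule returns the same answer, no significant difference. The intervals show that the two results carry very different information.

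**The case against.** The strongest case against the point has four parts.

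*The plan does not commit the fallacy.* A reader might infer that a favourable safety conclusion can rest only on a non-significant test. The documents do not support that. They contain no safety hypothesis and no safety decision rule, and they never say that a non-significant difference means the drug is safe. SAE definition, relatedness review and reporting are also planned in section 8.4. All of this stands. However, the section 8.4 review works case by case and does not compare arms, so the chi-squared test remains the only between-arm analysis stated for categorical safety data.

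*No single miss rate can be quoted as fact.* A reader might take about 70% as the chance of missing a doubling. It holds only at an assumed 20% versus 40%, with an assumed alpha and no correction. Section 8.4.1 counts every inpatient hospitalization as serious, so a high SAE rate is possible, and at 40% versus 80% the miss rate is only 25%. This stands, and it is why the range is shown.

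*Safety is secondary, and survival is not listed as safety.* Both are correct. Section 4.1 still sets a comparison of safety as part of the aim. Death is kept apart from the safety endpoints in the change proposed here.

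*Any 40-patient pilot has low power for safety, and nothing forbids reporting an interval.* This is also true. It favours estimation over testing and gives no reason for a larger sample. The remedy improves what is reported; it will not make the safety answer precise.

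**Conclusion.** The point holds as a gap in the analysis plan. Section 4.1 promises a comparison of safety, and Section 7 supplies for categorical safety data only a test of difference, with no estimate or interval. Under the stated assumptions the test misses a doubling of SAEs about 86% to 54% of the time for placebo rates of 10% to 30%, with 95% at a placebo rate of 5% and 25% at 40%. A non-significant result is therefore weak evidence on safety.

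The conclusion does not extend to saying that the plan equates non-significance with safety. The case for an interval does not depend on any one assumed SAE rate, because it concerns what the report can tell its reader about excess harm. This is a worthwhile, inexpensive improvement; it does not invalidate the design.

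**What to change.** In Section 7, take safety and survival out of the general chi-squared sentence and add text such as:

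> Safety endpoints (participants with at least one SAE, with at least one drug-related SAE, and with discontinuation of study drug for an adverse event) and death by 6 and by 12 months will be reported by arm as number and percent, with the risk difference and its two-sided 95% Newcombe (score) confidence interval. The largest excess risk that the interval does not exclude will be stated. Any chi-squared p-value is descriptive. A non-significant difference will not be interpreted as evidence of safety.

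In section 4.1, word the safety part of the aim as estimating the difference in risk between the arms.

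The cost is a few sentences in Section 7 and one phrase in section 4.1. SAEs, their relatedness and the reasons for discontinuation are already recorded under section 8.4, and survival is already an endpoint, so no extra patients, visits or data are needed. The downside is that the intervals will be wide, so the trial can make only a modest safety statement.
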